8.4 REPORTING PROCEDURES

8.4.1 ADVERSE EVENT REPORTING

Adverse Events will be documented on the appropriate Case Report Form (CRF) as the Investigator learns of the event. All AEs, not serious in nature, will be reviewed by the Sponsor during scheduled Interim Monitoring Visits (IMVs). The Investigator will follow all AEs until adequate resolution is achieved. The IRB should be notified of all AEs according to their notification policies.

All AEs will be reported to ACell Quality Assurance and reported under the appropriate regulatory consideration.

8.4.2 SERIOUS ADVERSE EVENT REPORTING

In the case of a SAE, the Investigator must immediately notify (within 1 working day of becoming aware of the event) the study Sponsor (contact information is provided in **Section 1, Key Roles**). The IRB must also be notified according to their notification policies.

All SAEs will be followed until satisfactory resolution or until the site Investigator deems the event to be chronic or the adherence to be stable. Other supporting documentation of the event may be requested by the DCC/study sponsor and should be provided as soon as possible. The study Sponsor will be responsible for notifying FDA of any unexpected fatal or life-threatening suspected adverse reaction as soon as possible but in no case later than 7 calendar days after the Sponsor's initial receipt of the information.

8.4.3 UNANTICIPATED ADVERSE DEVICE EFFECT REPORTING

An Investigator shall submit to the Sponsor and to the reviewing IRB a report of any UADE occurring during an investigation as soon as possible, but in no event later than 10 working days after the investigator first learns of the effect [21 CFR 812.150(a)(1)]. A Sponsor who conducts an evaluation of an UADE under 812.46(b) shall report the results of such evaluation to FDA and to all reviewing IRBs and participating investigators within 10 working days after the Sponsor first receives notice of the effect. Thereafter, the Sponsor shall submit such additional reports concerning the effect as FDA requests [21 CFR 812.150(b)(1)].

This study is not being conducted under an IDE; therefore, Sponsor reporting timelines may differ from those defined above.

8.4.4 REPORTING OF PREGNANCY

If a female becomes pregnant during this trial, she must be followed until the outcome of the pregnancy is known. Should she become pregnant during the follow-up visit period, no additional study devices will be placed.

9. CLINICAL MONITORING

Clinical site monitoring is conducted to ensure that the rights and well-being of human subjects are protected, that the reported trial data are accurate, complete, and verifiable, and that the conduct of the trial is in compliance with the currently approved protocol/amendment(s), with Good Clinical Practice (GCP), and with applicable regulatory requirement(s).

A Clinical Monitoring Plan will describe in detail who will conduct the monitoring, at what frequency monitoring will be done, at what level of detail monitoring will be performed, and the distribution of monitoring reports.

10. STATISTICAL CONSIDERATIONS

10.1 DESCRIPTION OF STATISTICAL METHODS

Wound area will be analyzed for size, percentage closure on weekly basis. The mean, median and standard deviations will be calculated and scatter plots developed to determine healing rates by application number, and days in treatment. The mean number of application of product will be tabulated.

All statistical tests to examine the change from baseline (study pre-treatment) will be conducted using a type 1 error rate of 5%. Simultaneous testing for the 2 primary endpoints will be conducted based on individual a priori thresholds. The analyses of the secondary endpoints will be conducted without adjustment for multiple testing.

The analysis of the primary endpoints will be based on a generalized linear model specifying the distribution as binomial. If a patient withdraws prior to completing the study, however the last recorded observation revealed the wound had closed, the patient will be counted in the primary analysis as having achieved complete wound epithelization. If a patient withdraws prior to the 12-week wound evaluation visit and the last recorded observation revealed the wound had not closed, the patient will be counted in the primary analysis as not having achieved complete wound epithelization. This procedure will also be followed for the examination of the patients by the various percent reduction thresholds. The analyses of all non-primary endpoints will be based on the distribution of data. For continuous variables, descriptive statistics will be used and the change from baseline will be tested against a difference of zero. For binomial and multinomial variables, results will be presented using counts, percentages, and shift tables. The analysis of the time of the initial observation of complete wound epithelization will be reported using Kaplan-Meier estimates. The sample size for this clinical investigation was derived based on establishing sufficient precision among the different endpoints to be able to reliably estimate the expected effect of the 2 product used either alone or in combination. For proportions, the length of the 2-sided 95% confidence interval from the proportion to the limit with 80 patients is between 9% and 10% (ref. table presented below).

Scenario	Lower 95% Exact Confidence Limit (%)	Percentage of Patients Who Respond	Upper 95% Exact Confidence Limit (%)
1	15.99	25.00	35.94
2	26.92	37.50	49.04
3	30.33	40.00	50.28
4	50.96	62.50	73.08
5	64.06	75.00	84.01

For mean changes from baseline, if the standard deviation of the difference from baseline for a parameter is 10 units, the confidence level will exceed 90% with a distance from the mean to the limit as small as 2 units.

For data derived from a binomial distribution and a continuous distribution, 80 patients should be sufficient to detect a clinically-meaningful change in this clinical investigation.

In summary, the sample size for this clinical investigation is sufficient to detect a 34% difference in the proportion of responders between the 2 treatments (power: 81.9%, alpha: 5%, 40 patients per treatment arm with 30% response and 64% response, respectively). If the observed proportion of response between the 2 treatment arms is 15% and 46% respectively, with 40 patients per treatment arm, the power will be 81.1%. If there is an imbalance between the 2 treatment arms (30 patients and 50 patients, respectively), and observed proportion of response between the 2 treatment arms is 15% and 47%, the power will be 80.3%.

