4.1.1 PRIMARY ENDPOINT

1. Effect of Cytal® with or without MicroMatrix® on primary measures of wound healing efficacy will be assessed by determining:

- a. Number and percentage of wounds with area reduced by greater than or equal to 40% by week 4, 60% by week 8, and 80% by week 12 as determined by wound image planimetry for each wound type.
- b. Number and percentage of completely healed wounds (100% epithelialization) by 12 weeks for each wound type. This will be verified by investigators and through a blinded review of wound photos by independent wound physicians.

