7.2.5 LONG-TERM FOLLOW UP VISIT & FINAL STUDY VISIT

(LTFU AT 26 WEEKS [182 DAYS] AND FSV AT 52 WEEKS [365 DAYS] FROM TREATMENT VISIT, ± 14 DAYS)

The following activities are required for the Long-Term Follow-Up Study Visit and the Final Study Visit:

1. Record any changes to employment and ambulatory status.
2. Document and update changes to concomitant medication log and medical history.
3. Record AEs as reported by participant or observed by Investigator.
4. Quality of Life Assessments (Katz ADL, W-QoL, VAS).
5. Perform a physical examination and wound SOC.
6. Perform delayed wound healing labs & procedures (PRN, as determined by the Investigator).
7. Collect updates to tobacco use.
8. Document laboratory results and ABI (as required) for lower extremity wounds (PRN at these visits, not required).
9. Perform closure and recurrence assessment.
10. Full wound evaluation and wound management.
 - a. Wound photos to include one zoomed in photo before debridement, at least one zoomed in photo after debridement (if performed). All photos taken in accordance with standardized wound care photography protocols.

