16. APPENDIX I: SCHEDULE OF EVENTS

Evaluation	Screening *	Treatment Visit	WEEKLY FOLLOW-UP VISITS												Week 26 (± 14 days) LTFU Visit	Week 52 (± 14 days) Final Study Visit	Unscheduled
			Week 1 (Visit 1)	Week 2 (Visit 2)	Week 3 (Visit 3)	Week 4 (Visit 4)	Week 5 (Visit 5)	Week 6 (Visit 6)	Week 7 (Visit 7)	Week 8 (Visit 8)	Week 9 (Visit 9)	Week 10 (Visit 10)	Week 11 (Visit 11)	Week 12 (Visit 12)			
Informed Consent	X																
Eligibility Assessment ¹	X	X															
Significant Medical, Surgical, Medication History	X																
Laboratory results & ABI (for lower extremity wounds) ²		X							X					X			X
Pregnancy test ³	X	X															
Employment & Ambulatory Status	X	X	X	X	X	X	X	X	X	X	X	X	X	X	X	X	X
Demographics, Social Info	X														X	X	
Physical Examination	X														X	X	X
Surveys (W-QoL, VAS, Katz)	X								X					X	X	X	
Independent 3 rd party wound assessment ⁴		X				X				X				X			
Wound photographs & planimetry ⁵	X	X	X	X	X	X	X	X	X	X	X	X	X	X			X
Delayed wound healing labs & procedures ⁶																	
Wound SOC activities	X	X	X	X	X	X	X	X	X	X	X	X	X	X	X	X	X
Wound evaluation ⁷	X	X	X	X	X	X	X	X	X	X	X	X	X	X			X
Wound management	X	X	X	X	X	X	X	X	X	X	X	X	X	X			X
Closure & Recurrence assessment			X	X	X	X	X	X	X	X	X	X	X	X	X	X	X
Cyral®/MicroMatrix® Applications ⁸		X	X	X	X	X	X	X	X	X	X	X	X	X			X
Study Wound related Adverse Events		X	X	X	X	X	X	X	X	X	X	X	X	X	X	X	X
Review Concomitant medications and Medical History		X	X	X	X	X	X	X	X	X	X	X	X	X	X	X	X
Biopsy and quantitative histopathology ⁹		X	X														

*--Screening Visit must occur within 7 days of Treatment Visit. The Screening Visit may be combined with the Treatment Visit, as long as all eligibility criteria have been confirmed prior to treatment.

1 – If Screening and Treatment Visits are not combined, verify that subject remains eligible prior to study device application (no need to repeat activities).

2 – ABI is PRN, as determined by the Investigator.

3 – Confirm a negative pregnancy test prior to study device application (test does not need to be repeated twice).

4 – Independent 3rd party expert will complete wound assessment as photographs are available. Additional assessments to be completed as appropriate.

5 – This is done through the use of the Silhouette Star camera system by Aranz®. To be completed at LTFU/FSV if applicable.

6 – PRN activity at all visits.

7 – Wound evaluations to be completed at LTFU/FSV if applicable.

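### The success branch of the withdrawal rule has no Week 12 limit, so a wound first closed after Week 12 can count towards the 12-week healing endpoint if the patient then withdraws

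*Combined protocol and SAP*

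**What the plan says.** Section 4.1.1 defines endpoint 1b as "Number and percentage of completely healed wounds (100% epithelialization) by 12 weeks for each wound type". The Protocol Summary defines it in the same way.

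Section 10.1, repeated in the Protocol Summary under Statistical Methodology, classifies withdrawals in two branches:

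- **Success:** "If a patient withdraws prior to completing the study, however the last recorded observation revealed the wound had closed". The patient is then counted in the primary analysis as having reached complete epithelialization.
- **Failure:** "If a patient withdraws prior to the 12-week wound evaluation visit and the last recorded observation revealed the wound had not closed". The patient is then counted as not having reached it.

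The rule is extended to endpoint 1a, the 40%, 60% and 80% area reductions at Weeks 4, 8 and 12: "This procedure will also be followed for the examination of the patients by the various percent reduction thresholds".

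Participation does not end at Week 12. The Protocol Summary (Participant & Study Duration) lists a Week 26 visit and a final visit at Week 52. At both, Section 7.2.5 requires staff to "Perform closure and recurrence assessment". Section 7.2.4 requires the same assessment at unscheduled visits, which can take place up to the final visit.

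**The concern.** The two branches cover different periods. The failure branch carries the endpoint's 12-week limit and the success branch does not. Because closure is still assessed after Week 12, the last recorded observation of a withdrawn patient can be a closure that came too late for the endpoint.

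Followed as written, two patients with the same wound course can receive different primary outcomes only because one of them later left the study. The error runs one way: after Week 12 the rule can turn a 12-week failure into a success but never the reverse.

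**Working it through.** No figure in the plan depends on this rule, so the main check is to set the provisions side by side.

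**1. What completing the study means.** The final visit is at Week 52 (Protocol Summary; Section 7.2.5). Section 5.3 ends enrollment in May 2019 and expects all subjects to have completed by May 2020, twelve months later. Completion is therefore Week 52, not Week 12.

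**2. Which visits can produce a case.** The wound must be open through Week 12, close later and be closed at the last observation, and the patient must withdraw before Week 52. The Week 26 visit and unscheduled visits after Week 12 can do this. A closure first seen at Week 52 cannot, because that patient has completed.

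**3. The same course under each provision.** Take a wound open at Week 12 and closed at Week 26.

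| Patient | Governing text | Primary outcome |
|---|---|---|
| Stays to Week 52 | Endpoint 1b, Section 4.1.1 | Not healed by 12 weeks |
| Withdraws at Week 30 | Success branch, Section 10.1 | Success |

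**4. Direction.** After the 12-week visit the failure branch no longer applies. If the wound closed by Week 12, reopened, and was open when the patient left at Week 30, neither branch applies and the endpoint definition governs. The rule can therefore only add successes after Week 12.

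**5. Size per patient.** The effect of one patient is 100/n points.

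- n = 80: 100/80 = 1.25 points. One, two or three patients add 1.25, 2.50 or 3.75 points.
- n = 100: 100/100 = 1.0 point. One, two or three patients add 1, 2 or 3 points.

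To place this on the plan's own scale, the exact (Clopper-Pearson) 95% interval for 20/80 = 25.00% is 15.99 to 35.94, which reproduces the first row of the Section 10.1 table. One reclassified patient gives 21/80 = 26.25% (17.04 to 37.29). Three give 23/80 = 28.75% (19.18 to 39.95).

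The endpoint is reported by wound type, so the shift within a type is larger. As an illustration only, assume an equal split over the six wound types named in Section 4.1. With 80 patients, 80/6 = 13.3 per type, and one patient is 100/13.3 = 7.5 points. With 100 patients, 100/6 = 16.7 per type, and one patient is 6.0 points.

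**6. Area-reduction thresholds.** The extension to endpoint 1a does not say how a last observation maps to Weeks 4, 8 and 12. Suppose a wound is below 40% reduction at Week 4, reaches 45% at Week 7, and the patient then withdraws. The text leaves it open whether the Week 7 value earns credit for Week 4. No size can be put on this from the documents.

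**The case against.** The strongest reply is that endpoint 1b is defined twice as healing by 12 weeks, and the withdrawal rule only explains how to count patients within that endpoint. A patient who attended Week 12 has an observed status, so there is nothing to impute. On this view the fault is a missing qualifier, and a sensible analyst would apply the 12-week limit anyway. The likely intent supports this: the wider success branch probably exists to keep patients who closed by Week 12 and left later. This stands as a statement of intent. However, no passage gives the definition priority, and the rule expressly governs how patients are counted in the primary analysis.

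It is also fair that the affected group is narrow. In addition, Section 10.1 states no numerical success threshold that one to three patients could cross.

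A reader might infer that late closures would escape the blinded photo review attached to endpoint 1b. The documents do not support that. The schedule marks the independent assessment at the Treatment Visit and Weeks 4, 8 and 12, but its footnote says "Independent 3rd party expert will complete wound assessment as photographs are available" and allows further assessments. Sections 7.2.4 and 7.2.5 require photographs at unscheduled visits and at Weeks 26 and 52. A route to verification exists.

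**Conclusion.** Wrong as written, but minor. The success branch lacks the time limit that the endpoint and the failure branch both carry, and literal use misclassifies a late closer who withdraws. Each such patient adds 1.25 points at n = 80 or 1.0 point at n = 100. The effect is zero if nobody closes after Week 12 and then withdraws. The conclusion assumes only that completing the study means Week 52, which the documents support.

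A reader might infer a sizeable bias by setting the rule against the expected dropout or the planned precision. Neither comparison is sound:

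- Section 5.3 expects 80 completers from at most 100 enrolled, after about 20% dropout. It does not say when patients leave or whether their wounds have closed, so the dropout figure does not estimate the number affected.
- Section 10.1 describes the distance from estimate to confidence limit as 9 to 10 points, but its own rows for 80 patients reach 49.04 − 37.50 = 11.54 points. The stated distance is not a reliable yardstick.

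The documents give neither withdrawal timing nor closure rates after Week 12, so no expected size can be stated.

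**What to change.** In Section 10.1 and in the Protocol Summary, replace both branches with one rule:

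- A patient who withdraws at any time counts as healed only if closure was first recorded at or before the Week 12 visit and the wound was closed at the last observation up to that point. If the Week 12 visit was missed, the cut-off is the end of the Week 12 visit window. Otherwise the patient counts as not healed by 12 weeks.
- For the 40%, 60% and 80% area reductions, use only observations up to the Week 4, Week 8 and Week 12 visits respectively.
- Report closures after Week 12 separately.

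Tying the cut-off to the visit keeps a Week 12 visit held a few days late, and the missed-visit clause covers patients who skip Week 12 and leave later. The Protocol Summary says that all visits have windows, but a width is given only for Weeks 26 and 52. The Week 12 window therefore needs to be written down.

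The change preserves the likely intent, since patients who closed by Week 12 and left later remain successes. It costs a few sentences in two places and needs no added visits, data or patients. The one drawback is that reported rates may be slightly lower than under the literal rule.

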	
 3. Subject is willing and able to adhere to protocol requirements and agrees to participate in the study program and comply with the study follow-up regimen. 4. Subject or legal representative is willing to provide informed consent. 5. For females of reproductive potential, confirmed negative pregnancy test at enrollment. 
Exclusion Criteria: (No exclusion criteria may meet for enrollment)
 
 1. Allergy or hypersensitivity to materials in porcine-based study products (per subject report) or personal preference. 2. Subject report of concurrent participation in another clinical trial that involves an investigational drug or device that would interfere with this study. 3. The subject has any physical or psychiatric condition that, in the Investigator's opinion, would warrant exclusion from the study or prevent the subject from completing the study. 4. The subject's wound shows evidence of infection as determined by the Principal Investigator (which may be indicated by presence of: elevated WBC, pus, moderate or greater discharge, abnormal odor, or acute osteomyelitis). 5. Wound with exposed organs or hardware. 6. Wound with burn etiology.
Number of Sites enrolling participants:	1 (NYU Winthrop Hospital)
ACell Study Products:	
 1. Cytal®™ Wound Matrix 1-Layer 2. MicroMatrix®
Participant & Study Duration:	
80 subjects are expected to complete this trial (maximum of 100 may be enrolled). The duration of participation for each subject will be up to a maximum of 55 weeks (1 week screening/treatment; 12 week follow-up; 26 week confirmation of wound closure/recurrence; 52 week final study visit). All visits have protocol stipulated windows.
 
Recruitment and enrollment efforts are expected to last for approximately 12 months, starting in June 2018. The study will end in approximately May 2019, with Last Subject Last Visit expected in May 2020.
 
The actual overall study duration or subject recruitment period may vary.

Statistical Methodology:	The objective of this study is to define the trajectory of healing using either 1 or 2 test products; the intra-patient change will be the focus

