	
of the analyses, not the comparison of response between 1 vs. 2 product application.
 
All statistical tests to examine the change from baseline (study pre-treatment) will be conducted using a type 1 error rate of 5%. Simultaneous testing for the 2 primary endpoints will be conducted based on individual a priori thresholds. The analyses of the secondary endpoints will be conducted without adjustment for multiple testing.
 
The analysis of the primary endpoints will be based on a generalized linear model specifying the distribution as binomial. If a patient withdraws prior to completing the study, however the last recorded observation revealed the wound had closed, the patient will be counted in the primary analysis as having achieved complete wound epithelization. If a patient withdraws prior to the 12-week wound evaluation visit and the last recorded observation revealed the wound had not closed, the patient will be counted in the primary analysis as not having achieved complete wound epithelization. This procedure will be also be followed for the examination at the patients by the various percent reduction thresholds. The analyses of all non-primary endpoints will be based on the distribution of data. For continuous variables, descriptive statistics will be used and the change from baseline will be tested against a difference of zero. For binomial and multinomial variables, results will be presented using counts, percentages, and shift tables. The analysis of the time of the initial observation of complete wound epithelization will be reported using Kaplan-Meier estimates.

--	--

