4. STUDY DESIGN AND ENDPOINTS

4.1 DESCRIPTION OF THE STUDY DESIGN

This study is a single-site, prospective, observational study of Cytal® Wound Matrix alone or in combination with MicroMatrix® for management of wounds. Cytal® and MicroMatrix® both consist of decellularized porcine urinary bladder matrix (UBM). The processed UBM retains native extracellular matrix structure with intact epithelial basement membrane and numerous collagens that may promote improved wound healing. Cytal® consists of single- or multilayer sheets of UBM, while MicroMatrix® is a micronized powder form of UBM. Both products are FDA 510k cleared (K152721 and K060888) for use in the management of wounds.

In this study, Cytal® Wound Matrix 1-Layer will be applied to study wounds, with MicroMatrix® applied topically to fill the base of deep wounds (exceeding 3mm in depth) according to product use instructions. Patients with diverse wound types will be observed in the study, including but not limited to patients with venous ulcers, diabetic foot ulcers, pressure ulcers, trauma wounds, external surgical wounds, and wound dehiscence/surgical site infection.

Patients may undergo weekly treatment for their wounds and can be treated with up to 10 applications of Cytal® (with MicroMatrix® when wound depth exceeds 3mm) within the first 12 weeks. If the Subject has multiple wounds, the most-appropriate wound that meets inclusion criteria and has at least two cm of healthy tissue between itself and other wounds (as determined by the investigator) will be selected as the Study Wound. A protocolized standard of care will be followed for Study Wounds in addition to the application of Cytal® and MicroMatrix® (i.e. surgical debridement, offloading etc. as appropriate for the particular wound type and severity).

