8 – Study device may be applied no more than 10 times total. This includes one (1) application at the Treatment Visit, and up to nine (9) additional applications throughout FUV 1-12 and unscheduled visits.

- 9 - Pathology on biopsy – For Normally healing wounds: Biopsies to be completed before debridement and product application at Initial Treatment Visit, Visit 1, and a third and final biopsy to be obtained at timepoint determined by the Investigator. For delayed healing wounds: Biopsies to be completed before debridement and product application at Initial Treatment, Visit 1, Visit 4, and a fourth and final biopsy at ~70-90% wound closure.
- 10 – Surveys will also be completed at time of healing.

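### Section 10.1 claims to estimate, and powers, effects of the two products that the design cannot identify, and it conflicts with the synopsis, which sets that comparison aside

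*Combined protocol and SAP*

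**What the plan says.** **Products.** Section 4.1 applies Cytal to all study wounds and adds MicroMatrix to deep ones. A patient "can be treated with up to 10 applications of Cytal® (with MicroMatrix® when wound depth exceeds 3mm) within the first 12 weeks". Footnote 8 to the Schedule of Events (Appendix I) splits the maximum of 10: "This includes one (1) application at the Treatment Visit, and up to nine (9) additional applications throughout FUV 1-12 and unscheduled visits". Section 7.2.3 makes the follow-up applications as-needed.

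**Sample size.** Section 10.1 says the number of patients gives enough precision "to be able to reliably estimate the expected effect of the 2 product used either alone or in combination". It closes by calling the sample size "sufficient to detect a 34% difference in the proportion of responders between the 2 treatments". The inputs listed for this first case are "power: 81.9%, alpha: 5%, 40 patients per treatment arm with 30% response and 64% response, respectively". Two further cases follow: 15% versus 46% with 40 per arm (power 81.1%), and 15% versus 47% with 30 and 50 patients (power 80.3%).

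**Aim.** The Protocol Summary (Statistical Methodology) says the study is to "define the trajectory of healing using either 1 or 2 test products". It then makes change within patients the focus "of the analyses, not the comparison of response between 1 vs. 2 product application". Section 10.1 does not repeat that sentence.

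**Endpoints and model.** Section 4.1.1 reports the primary endpoints by wound type, for Cytal with or without MicroMatrix. The binomial model in Section 10.1 names no term for product or depth.

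**The concern.** The power text needs two groups of patients, but the protocol assigns none and gives no rule for forming them. A wound that starts deep can receive both products early and Cytal alone later, and a shallow wound that deepens can go the other way. An analyst who follows Section 10.1 must decide after the fact which group such a wound belongs to.

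That decision can produce a difference by itself. Whether a wound is still deeper than 3 mm late in the course depends on how well it is healing. A group defined by late or predominant use of the combination therefore collects wounds that are not filling. At stake is a difference in healing between one and two products that readers take for a product effect, supported by a power statement that appears to license that reading.

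**Working it through.** **1. The stated power.** Two-sided comparison of two proportions, pooled variance under the null, continuity correction c = 0.5(1/n1 + 1/n2). The protocol does not give the sidedness of this test; I assume two-sided.

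Power = Φ[(d − c − 1.96·se0)/se1]. For 30% versus 64%, 40 per arm:
- d = 0.34; c = 0.025; pooled p = 0.47
- se0 = √(0.47 × 0.53 × 2/40) = 0.1116
- se1 = √((0.30 × 0.70 + 0.64 × 0.36)/40) = 0.1049
- (0.34 − 0.025 − 1.96 × 0.1116)/0.1049 = 0.917, so power = 82.05% (stated 81.9%)

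The same formula gives 80.5% for 15% versus 46% (stated 81.1%), and 79.0% or 81.2% for 30/50, depending on which arm has 30 (stated 80.3%). The arithmetic is acceptable. What is missing is a definition of the arms.

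**2. What the design can identify.**
- MicroMatrix alone: no wound receives it, so its effect alone cannot be estimated.
- Cytal alone versus the combination at first application: the 3 mm rule separates the groups completely on entry depth, so a product difference and a depth difference cannot be told apart.
- Groups by product used during follow-up: the depth condition is attached to a course of up to 10 applications. The natural reading, though not stated in so many words, is that it is applied each time. Membership then depends on depth after baseline, and so on healing.

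**3. Illustration with no product effect.** None of these inputs come from the documents. Entry depth is lognormal with median 3 mm and log SD 0.6. Remaining wound fraction is exp(−λt), with λ lognormal (median 0.22 per week, log SD 0.4). Depth follows that fraction with noise (log SD 0.2). A wound is healed when the fraction falls below 5%. Applications are weekly from Week 0 to Week 9, until healing. Entry depth is not prognostic.

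| Grouping rule | Healed, combination | Healed, Cytal alone | Share in combination |
|---|---|---|---|
| First application (by entry depth) | 37.7% | 37.6% | 49.8% |
| Ever used MicroMatrix | 36.7% | 38.7% | 52.4% |
| Used at most applications | 7.8% | 39.5% | 5.7% |
| Last application | 0.2% | 38.0% | 1.0% |

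With more variable healing rates (log SD 0.7) the pairs are 43.1/43.7, 41.3/45.8, 5.4/46.7 and 0.3/44.6. If deeper wounds also heal more slowly (λ multiplied by (depth/3) to the power −0.3), the first-application rule gives 25.7% versus 51.3%, or 34.8% versus 51.0% with log SD 0.7. That gap is pure confounding by depth.

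**4. Sensitivity to the number of applications.** A second assumed model, again with no product effect: entry depth uniform from 0.5 to 6 mm, weekly slope N(−0.35, 0.35) mm, noise SD 0.3 mm, closure when depth reaches zero. Grouping by last product, Cytal alone versus combination:
- 1 application: 73% versus 48% (identical to entry depth)
- 3 weekly applications: 78% versus 33%
- 4 weekly applications: 80% versus 22%
- weekly through Week 9: 75% versus 0%

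In this model ever-use gives 76% versus 46% with 3 applications and 82% versus 44% with weekly applications through Week 9.

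**5. Precision of strata.** Exact 95% limits around a 40% response:
- n = 30: 22.7% to 59.4% (17.3 and 19.4 points)
- n = 40: 24.9% to 56.7% (15.1 and 16.7 points)
- n = 50: 26.4% to 54.8% (13.6 and 14.8 points)
- n = 80: 29.20% to 51.56% (10.8 and 11.6 points)

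The protocol's table prints 30.33 to 50.28 for 40%, which is the exact interval for 40 of 100, so I use 32 of 80 here.

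**The case against.** The best defence is that the plan schedules no analysis by product. The synopsis sets the one-versus-two-product comparison aside, the primary endpoints are by wound type, and the quoted clause is a rationale for sample size followed by precision for all 80 patients. This stands as far as it goes. A reader might infer that the plan promises product-specific results; taken whole, the documents do not support that. But Section 10.1 omits the disclaimer and powers the very contrast that the synopsis sets aside. The disclaimer therefore creates a conflict to be reconciled, and it supplies no rule for classifying a wound.

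Two other stronger readings also fail. A reader might infer that every grouping by product sorts wounds by how they healed. Grouping by first product does not: it depends only on entry depth, and its fault is confounding. A reader might also infer that the combination is never in use just before closure. Applications are optional and as-needed, so a wound could receive its last one above 3 mm and close later under standard care. The near-zero healing rates under the last-product rule come from assuming a long weekly course.

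Finally, all the sizes are assumed. The documents give no depth distribution, no rate of changing product and no relation of depth to healing. The ever-use gap is only 2 to 4.5 points in the first model, and the extreme rows there concern 1.0% to 5.7% of wounds.

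**Conclusion.** The point holds as a conflict within the plan and a limit of the design. Section 10.1 claims reliable estimation of product effects and states power for a two-arm contrast. The design has no arms, no MicroMatrix-alone use, no overlap in entry depth between the two uses, and no rule for a wound whose product changes. Any contrast by product reflects entry depth. If product is classified during follow-up, it also reflects healing: potentially strongly for product used most or last, and less so, depending on the assumptions, for ever-use.

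The size of the bias cannot be derived from the documents. The illustrations show only that the choice of rule can move the difference from about zero to more than 30 points with no product effect (39.5 − 7.8 = 31.7), close to the 34 points in the power statement. That rests on weekly application and on depth falling with healing. The main estimates by wound type, for Cytal with or without MicroMatrix, are not affected by this problem.

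**What to change.** - Reconcile Section 10.1 with the synopsis. Replace the quoted clause with: *to estimate the healing rate of wounds managed with Cytal, with MicroMatrix added according to depth*.
- Remove the two-arm power text at the end of Section 10.1, or relabel it so that it cannot be read as power for a product effect.
- If results by product are shown, group wounds by depth (not exceeding 3 mm, exceeding 3 mm) recorded at the Treatment Visit before the first application. State whether that depth is taken before or after debridement. Keep each wound in its stratum throughout, tabulate later changes of product as counts, and state that the strata are descriptive and are not effects of either product.

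This changes analysis wording only, not treatment. The costs are that wounds that change product stay in their entry stratum, and that stratum intervals are wider: about 14 to 19 points per side with 30 to 50 wounds, against about 11 to 12 for all 80, around a 40% response. The sponsor must also confirm that entry depth is captured as data. Applying the 3 mm rule requires assessing depth, but the Schedule of Events lists planimetry and wound evaluation without naming a depth field.
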